7.1.14 Correlative Studies

Three different tests will be performed during the course of the trial. At screening, samples will be collected from bone marrow aspirate and peripheral blood. If determined the subject has extramedullary disease (as permitted in inclusion criterion #4), biopsy of the involved area will be the method by which correlative samples will be obtained. Biopsy will involve at least 6 core biopsies from the disease sites. If the biopsy of an extramedullary site is considered to put the subject at considerable risk, the subject may still participate in the trial without collection of the correlative samples. At the day 28 time point, the samples will be obtained from peripheral blood. Correlatives will be performed at investigator's discretion if early study termination. For sampling requirements, see Section 7.2.

7.1.15 CSF for ALL Involvement/IT Chemotherapy

If a potential study subject demonstrates clinical signs or symptoms of CNS involvement, a CSF sample will be obtained through a spinal tap. If CNS involvement is confirmed, the subject will not be eligible for study participation. Provided there are no contra-indications, prophylactic intrathecal methotrexate will be administered per standard of care, 7-10 days after initiation of CPX dosing.

7.1.16 Imaging

If a study subject is found to have extramedullary disease as permitted by inclusion criterion #4, the method for baseline disease assessment will be CT or PET/CT scan per standard of care. This method will also be used for determining response assessment on Day 28.

7.2 LABORATORY PROCEDURES/EVALUATIONS

7.2.1 CLINICAL LABORATORY EVALUATIONS

- **Hematology:** hemoglobin, hematocrit, white blood cells (WBC) with differential count, platelet count.
- **Metabolic Panel:** albumin, BUN, alkaline phosphatase, CO2, calcium, chloride, glucose, potassium, sodium, total protein, LDH, uric acid, magnesium, phosphorus, creatinine, total bilirubin, alanine aminotransferase (ALT), aspartate aminotransferase (AST).

- **Urinalysis:** complete urinalysis with microscopic evaluation
- **Pregnancy test:** to be done within 24 hours prior to study intervention and results must be available prior to administration of study product.
- Laboratory testing on day one and during the hospitalization period, EOT, and follow-up will be at physician discretion per standard of care.

7.2.2 OTHER ASSAYS OR PROCEDURES

1. To explore the activity of CPX-351 *ex vivo* using live image capture in a reconstituted tumor micro-environment (EVOS system) as a potential biomarker for response: Primary patient ALL cells will be seeded into a 384-well plate onto reconstructed TME, which includes extracellular matrix (collagen 1) and human bone marrow derived stromal cells (BMSC). CPX-351 dosed at 5 different concentrations will be added to the media, and plate is then continuously imaged for 96 hours. A digital image analysis algorithm detects tumor cells based on cell size and membrane motion. Changes in viability are quantified by area under curve (AUC). HBL-2 cells are used as a control.
2. To identify potential drug candidates for future combinatorial approaches, including assessment of the T-cell repertoire, PDL1 expression by conventional immunohistochemistry, and BH3 profiling.
T-cell assessment: Leukocytes will be isolated from BMBx aspirate sample by Ficoll-Hypaque gradient separation from RBCs (and other stromal elements, in the case of BMBx aspirate samples). Cells will be enumerated after 2 washes in PBS and allocated for flow cytometric analysis or for *ex vivo* culture in stimulation conditions. Cells will be aliquoted into 200,000 cell fractions in preparation for subsequent analysis. Leukocytes from each patient sample will be stained with fluorochrome-conjugated antibodies according to each of 3 analysis panels. Panels have been designed to assess lymphocytes subsets, effector/memory maturation, and exhaustion.
3. PDL1 expression: Will be determined on blasts/stroma using Dako antibody on formalin fixed paraffin embedded bone marrow core biopsy slides per routine.
4. BH3 Profiling: Briefly following membrane permeabilization with digitonin, BH3 mimetic peptides targeting BIM, BAD, HRK, and MS-1 will be used to interrogate the contribution of BCL2, BCLXL, and MCL1 to mitochondrial outer membrane permeabilization (MOMP). The collapse of the transmembrane mitochondrial potential is used as a surrogate for MOMP, and estimated by fluorescence following rhodamine dye accumulation.
5. Sampling of extramedullary disease will involve CT guided or excisional biopsy collection of 6 core biopsy samples (if possible), to be divided evenly between the two investigators' laboratories assigned to perform the above tests. This will be done in accordance with the Moffitt Total Cancer Care (TCC) protocol.

7.3 STUDY SCHEDULE

7.3.1 SCREENING

Screening Visit (Day -28 to -1)

- Obtain and review medical history to determine eligibility based on inclusion/exclusion criteria.

- Written informed consent to be obtained prior to any screening procedures
- Review medications history (including over-the-counter drugs, vitamins, herbs, alcohol) to determine eligibility based on inclusion/exclusion criteria.
- Perform physical examination needed to determine eligibility based on inclusion/exclusion criteria
- Vital signs measurements
- Evaluation of ECOG performance status
- Twelve-lead ECG and Echocardiogram or MUGA.
- Serum beta-human chorionic gonadotropin (β -hCG) pregnancy test for women of childbearing potential
- Clinical laboratory testing including urinalysis, serum chemistry, hematology, and coagulation parameters. Clinical assessments (laboratory tests, ECHO/MUGA, EKG) performed as part of the subject's routine clinical evaluation and not specifically for this study need not be repeated after signed informed consent has been obtained provided the assessments fulfill the study requirements and are performed within 28 days of starting study treatment.
- Bone marrow biopsy and peripheral blood sample will need to be repeated in order to collect correlative samples.
- CT or PET/CT scan of affected areas for subjects determined to have extramedullary disease or for staging purposes prior to treatment.
- Spinal tap if subject is determined to be symptomatic for CNS involvement

7.3.2 ENROLLMENT/BASELINE/STUDY VISITS

7.3.2.1 Induction Baseline Visit (Day 1)

- In-patient admission
- Verify subject still meets inclusion/exclusion criteria.
- Review results of serum pregnancy test, if applicable.
- Assess and record baseline symptoms prior to study drug administration.
- CBC with differential
- Chemistry profile (ALT, AST, alkaline phosphatase, total bilirubin, calcium, bicarbonate, sodium, potassium, chloride, creatinine, BUN, total protein and albumin)
- LDH, uric acid, magnesium, phosphorus
- Initiation of induction therapy- study drug administration (CPX-351 intravenously)

7.3.2.2 Induction Day 2

- CBC with differential
- Chemistry profile (ALT, AST, alkaline phosphatase, total bilirubin, calcium, bicarbonate, sodium, potassium, chloride, creatinine, BUN, total protein and albumin)
- LDH, uric acid, magnesium, phosphorus

7.3.2.3 Induction Day 3

- CBC with differential
- Chemistry profile (ALT, AST, alkaline phosphatase, total bilirubin, calcium, bicarbonate, sodium, potassium, chloride, creatinine, BUN, total protein and albumin)
- LDH, uric acid, magnesium, phosphorus
- Study drug administration (initiation of CPX-351 intravenously)

7.3.2.4 Induction Day 4

- CBC with differential
- Chemistry profile (ALT, AST, alkaline phosphatase, total bilirubin, calcium, bicarbonate, sodium, potassium, chloride, creatinine, BUN, total protein and albumin)
- LDH, uric acid, magnesium, phosphorus

7.3.2.5 Induction Day 5

- CBC with differential
- Chemistry profile (ALT, AST, alkaline phosphatase, total bilirubin, calcium, bicarbonate, sodium, potassium, chloride, creatinine, BUN, total protein and albumin)
- LDH, uric acid, magnesium, phosphorus
- Study drug administration (initiation of CPX-351 intravenously)

7.3.2.6 Induction Day 6

- CBC with differential
- Chemistry profile (ALT, AST, alkaline phosphatase, total bilirubin, calcium, bicarbonate, sodium, potassium, chloride, creatinine, BUN, total protein and albumin)
- LDH, uric acid, magnesium, phosphorus

7.3.2.7 Induction Day 7

- CBC with differential

- Chemistry profile (ALT, AST, alkaline phosphatase, total bilirubin, calcium, bicarbonate, sodium, potassium, chloride, creatinine, BUN, total protein and albumin)
- LDH, uric acid, magnesium, phosphorus
- Peripheral blood sample for correlative studies
- CSF sample/IT chemo (if no contraindications, will be performed day 7-10 see Section 7.1.15)

7.3.2.8 Induction Day 10

- CBC with differential
- Chemistry profile (ALT, AST, alkaline phosphatase, total bilirubin, calcium, bicarbonate, sodium, potassium, chloride, creatinine, BUN, total protein and albumin)
- LDH, uric acid, magnesium, phosphorus
- CSF sample/IT chemo (if not performed on day 7, 8, or 9)
- Continuous hospitalization until determined to have acceptable bone marrow recovery

7.3.2.9 Induction Day 28

- CBC with differential
- Chemistry profile (ALT, AST, alkaline phosphatase, total bilirubin, calcium, bicarbonate, sodium, potassium, chloride, creatinine, BUN, total protein and albumin)
- LDH, uric acid, magnesium, phosphorus
- Bone marrow biopsy, if bone marrow biopsy is positive at screening
- CT or PET/CT scan of affected areas for response assessment for subjects with extramedullary disease
- Peripheral blood sample for correlative studies

7.3.2.10 Induction Day 29 +

- Continuous hospitalization until determined to have acceptable bone marrow recovery
- Laboratory testing continues per standard of care until hospital discharge

7.3.2.11 First Consolidation Therapy Day 1

- Subject has documented response (CR, Cri, or PR, see Appendix A), or in the opinion of the principal investigator is showing clinical benefit with adequate count recovery (ANC > 500/ μ L and platelets > 50,000/ μ L).
- CBC with differential

- Chemistry profile (ALT, AST, alkaline phosphatase, total bilirubin, calcium, bicarbonate, sodium, potassium, chloride, creatinine, BUN, total protein and albumin)
- Day 1 must be given 28 days-75 days after start of induction
- Study drug administration (initiation of CPX-351 intravenously)

7.3.2.12 First Consolidation Therapy Day 3

- CBC with differential
- Chemistry profile (ALT, AST, alkaline phosphatase, total bilirubin, calcium, bicarbonate, sodium, potassium, chloride, creatinine, BUN, total protein and albumin)
- Study drug administration (initiation of CPX-351 intravenously)

7.3.2.13 First Consolidation Day 28

- CBC with differential
- Chemistry profile (ALT, AST, alkaline phosphatase, total bilirubin, calcium, bicarbonate, sodium, potassium, chloride, creatinine, BUN, total protein and albumin)
- LDH, uric acid, magnesium, phosphorus
- Bone marrow biopsy, if bone marrow biopsy is positive at screening
- CT or PET/CT scan of affected areas to assess response for subjects with extramedullary disease

7.3.2.14 Second, and Third Consolidation Therapy Day 1

- Subject has documented response (CR, CRi, or PR, see Appendix A), or in the opinion of the principal investigator is demonstrating clinical benefit with adequate count recovery (ANC > 500/ \square L and platelets > 50,000/ \square)
- CBC with differential
- Chemistry profile (ALT, AST, alkaline phosphatase, total bilirubin, calcium, bicarbonate, sodium, potassium, chloride, creatinine, BUN, total protein and albumin)
- Echocardiogram will be repeated for any patient with >550mg/m² daunorubicin (or daunorubicin anthracycline equivalent) exposure. Therapy will only be permitted if the ejection fraction remains >50% and without >10% decrease in ejection fraction from baseline.
- Day 1 must be given 28 days-56 days after start of the previous consolidation
- Study drug administration (initiation of CPX-351 intravenously)

7.3.2.15 Second and Third Consolidation Day 3

- CBC with differential
- Chemistry profile (ALT, AST, alkaline phosphatase, total bilirubin, calcium, bicarbonate, sodium, potassium, chloride, creatinine, BUN, total protein and albumin)
- Study drug administration (initiation of CPX-351 intravenously)

7.32.16 Second and Third Consolidation Day 28

- CBC with differential
- Chemistry profile (ALT, AST, alkaline phosphatase, total bilirubin, calcium, bicarbonate, sodium, potassium, chloride, creatinine, BUN, total protein and albumin)
- LDH, uric acid, magnesium, phosphorus
- Bone marrow biopsy, if bone marrow biopsy is positive at screening
- CT or PET/CT scan of affected areas to assess response for subjects with extramedullary disease

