5 STUDY ENROLLMENT AND WITHDRAWAL

5.1 PARTICIPANT INCLUSION CRITERIA

Patients must meet all of the following criteria to be eligible for study entry:

1. Be willing and able to provide written informed consent/assent for the trial.
2. Be ≥ 18 years of age on day of signing informed consent.
3. Able to adhere to the study visit schedule and other protocol requirements.
4. Pathologically confirmed B- or T-cell acute lymphoblastic or mixed phenotype acute leukemia, with $\geq 5\%$ peripheral blood or bone marrow lymphoblasts and/or extramedullary disease $>1 \times 1 \text{ cm}$.
5. Relapsed or refractory acute lymphoblastic leukemia after at least 1 prior cycle of therapy. Patients with Philadelphia chromosome positive disease must have failed at least two prior tyrosine kinase inhibitors.
6. Eastern Cooperative Oncology Group (ECOG) performance status 0-1.
7. Cardiac ejection fraction $\geq 50\%$ by echocardiography or MUGA.
8. Must be at least 2 weeks out from any prior systemic chemotherapy, blinatumumab, radiation, and/or other investigational agents, and have recovered to grade 1 from any toxicity related to prior therapy. Glucocorticoids are permitted up to 1 day prior to the first dose.
9. Serum bilirubin and creatinine $\leq 1.5 \times$ upper limit of normal (ULN). AST and ALT must be $\leq 3 \times$ ULN, unless there is suspected liver involvement.
10. Females of childbearing potential (FCBP) must have a negative serum pregnancy test at screening. A FCBP is considered when a sexually mature female: 1) has not undergone a hysterectomy or bilateral oophorectomy; or 2) has not been naturally postmenopausal for at least 12 consecutive months.
11. A FCBP must agree to use of two methods of highly effective contraception, be surgically sterile, or abstain from heterosexual activity for the course of the study through 30 days after the last dose of study treatment.
12. Male subjects must agree to use an adequate method of contraception starting with the first dose of study therapy through 30 days after the last dose of study therapy. Men must agree to not donate sperm during and after the study

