5.2 PARTICIPANT EXCLUSION CRITERIA

Any of the following is a criterion for exclusion from the study:

1. Clinical evidence of active central nervous system (CNS) leukemia.
2. Any major surgery or radiation therapy within four weeks.
3. Any active infection requiring systemic therapy, including HIV, Hepatitis B, and/or Hepatitis C.
4. Has a history or current evidence of any condition, therapy, or laboratory abnormality that might confound the results of the trial, interfere with the subject's participation for the full duration of the trial, or is not in the best interest of the subject to participate, in the opinion of the treating investigator (including but not limited to severe graft-versus-host disease, unstable angina, pulmonary hypertension, active/prior veno-occlusive disease of the liver, or severe CHF (NYHA III-IV).
5. Patients with active (uncontrolled, metastatic) second malignancies are excluded.
6. Is pregnant or breastfeeding, or expecting to conceive or father children within the projected duration of the trial, starting with the screening visit through 30 after the last dose of trial treatment.
7. Hypersensitivity to cytarabine, daunorubicin, or liposomal products.
8. History of Wilson's disease or other copper-metabolism disorder.
9. Patients with prior cumulative anthracycline exposure of greater than 368 mg/m² daunorubicin (or equivalent).

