8.4.4 EVENTS OF SPECIAL INTEREST

1. **Cardiotoxicity:** Current studies estimate the risk of cardiotoxicity to be low, perhaps related to the liposomal formulation. However, given that patients will have likely had prior anthracycline exposure (up to a maximum of 368 mg/m² daunorubicin or equivalent), we will obtain baseline echocardiogram or MUGA to ensure adequate ejection fraction. Followup echocardiogram or MUGA will be performed in all patients with symptomatic heart failure, defined as follows: worsening 1) dyspnea on exertion, 2) orthopnea, and/or 3) paroxysmal nocturnal dyspnea - with following concomitant findings of fluid overload on exam not well explained by prior therapy (such as hydration related to an episode of sepsis), including: 1) development of a third heart sound, 2) jugular venous distention with positive hepatojugular reflex, 3) pulmonary rales, and/or 4) lower extremity edema (ref 31). Follow-up echocardiogram or MUGA prior to each cycle of consolidation will be performed for all patients exceeding 550 mg/m² daunorubicin (or equivalent) . Patients with an ejection fraction of <50% or a decrease of >10% from baseline will discontinue consolidation therapy. The development of symptomatic heart failure and/or decrease in ejection fraction to <50%, or >10% from baseline will be reported to Jazz Pharmaceuticals.
2. **Bone marrow aplasia:** Liposomal delivery of chemotherapy may facilitate increased deposition within hematopoietic stem cells, culminating in delay or failure to recover hematopoietic cell reconstitution following therapy. In particular, a hypocellular marrow without adequate count recovery >42 days from start of induction or consolidation cycles will be reported to the sponsor.

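### At an ejection fraction of exactly 50%, section 7.3.2.14 and footnote l bar further consolidation, but the stop in section 8.4.4 is not met

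*Combined protocol and SAP*

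**What the plan says.** Three places state a continuation rule based on ejection fraction (EF).

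- **Section 7.3.2.14** (second and third consolidation, Day 1): "Echocardiogram will be repeated for any patient with >550mg/m² daunorubicin (or daunorubicin anthracycline equivalent) exposure". The next sentence reads "Therapy will only be permitted if the ejection fraction remains >50% and without >10% decrease in ejection fraction from baseline".
- **Section 7.3.7, footnote l** repeats both sentences and names no cycle.
- **Section 8.4.4** (cardiotoxicity): "Patients with an ejection fraction of <50% or a decrease of >10% from baseline will discontinue consolidation therapy". The sentence before it reads "Follow-up echocardiogram or MUGA prior to each cycle of consolidation will be performed for all patients exceeding 550" mg/m². The same EF limits also trigger a report to the drug supplier.

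Three other places bear on the point. Inclusion criterion 7 (section 5.1) sets the entry EF at 50% or more. Exclusion criterion 9 (section 5.2) caps prior anthracycline exposure at 368 mg/m² daunorubicin equivalent. The list under "7.3.2.11 First Consolidation Therapy Day 1" covers response or benefit with count recovery, blood tests, the time window and drug administration. It contains no cardiac imaging and no EF condition.

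**The concern.** Section 7.3.2.14 and footnote l say when therapy is permitted, and section 8.4.4 says when it ends. The two should be complements, but a reading of exactly 50% falls outside both: it is not above 50, and it is not below 50. The value is not arbitrary, because 50% is the protocol's own entry boundary. A patient admitted at 50% can never satisfy a requirement that EF remain above 50% unless it rises.

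This is a cardiac stopping rule in patients whom the protocol expects to have had anthracyclines already. Staff working from the visit list would withhold the cycle, while staff working from section 8.4.4 would find no reason to stop. Section 10.4.4 plans a table of adverse events leading to discontinuation of study drug and of events of special interest. With 10 planned patients, one patient classified differently is 1/10, or 10 percentage points.

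**Working it through.** The plan gives no figure to reproduce. The check sets the two rules side by side and finds where they disagree.

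**1. The rules at and around 50%.** Let B be baseline EF and E the current EF. Read the fall first as percentage points, B − E.

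- Rule A (7.3.2.14 and footnote l): treat only if E > 50 and B − E is not > 10.
- Rule B (8.4.4): stop if E < 50 or B − E > 10.

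| B | E | Fall (points) | Rule A | Rule B |
|---|---|---|---|---|
| 50 | 49 | 1 | barred | stop |
| 50 | 50 | 0 | barred | no stop |
| 50 | 51 | none | permitted | no stop |
| 55 | 50 | 5 | barred | no stop |
| 60 | 50 | 10 | barred | no stop |
| 60 | 49.9 | 10.1 | barred | stop |
| 62 | 51 | 11 | barred | stop |

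The rules part only at E = 50, and only when the fall is not itself more than 10%.

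- Percentage points: B − 50 ≤ 10, so B runs from 50 to 60.
- Relative change: (B − 50)/B ≤ 0.10, so B ≤ 50/0.9 = 55.6.

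Above those baselines both rules bar a reading of 50%.

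**2. Who reaches the check.** Rule A is tied to exposure above 550 mg/m². Exposure on study depends on c, the mg of daunorubicin per unit, which the documents do not give. Doses are from section 6.1.7: induction 3 × 100 = 300 u/m², each consolidation 2 × 65 = 130 u/m². At the entry cap of 368 mg/m² with full doses, 550 is passed:

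- before consolidation 1 if 368 + 300c > 550, so c > 182/300 = 0.607;
- before consolidation 2 if 368 + 430c > 550, so c > 182/430 = 0.423;
- before consolidation 3 if 368 + 560c > 550, so c > 182/560 = 0.325.

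Maximum exposure (mg/m²) over an assumed range of c:

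| c | Before cycle 1 | Before cycle 2 | Before cycle 3 |
|---|---|---|---|
| 0.3 | 458 | 497 | 536 |
| 0.4 | 488 | 540 | 592 |
| 0.5 | 518 | 583 | 648 |
| 0.6 | 548 | 626 | 704 |
| 0.7 | 578 | 669 | 760 |

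Less prior exposure than the cap would need a larger c. The cycle 1 column shows when the missing cardiac step in 7.3.2.11 could matter. The other two show when the conflict at 50% can arise in cycles 2 and 3.

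**3. The meaning of 10%.** Take B = 60. A relative fall of more than 10% means E < 60 × 0.9 = 54. A fall of more than 10 points means E < 60 − 10 = 50.

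- Under 8.4.4 the two meanings give different answers for 50 ≤ E < 54.
- Under 7.3.2.14 and footnote l they differ for 50 < E < 54, because 50 is barred on either meaning.
- A reading of 54 is not affected: a fall of exactly 10% is not more than 10%.

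**The case against.** The strongest reply is that the two instructions can both be obeyed. Section 8.4.4 lists reasons to stop and does not say that a patient at 50% may be dosed. Withholding the cycle satisfies every passage. That is correct, so a reader should not infer that 8.4.4 authorises treatment at 50%. What stands is that 8.4.4, read alone, gives no reason to stop a patient whom 7.3.2.14 and footnote l bar.

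Several stronger readings are tempting but not supported:

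- *Any patient measured at 50% is affected.* No. The patient must also be above 550 mg/m², be due consolidation, and have a fall of not more than 10%.
- *The mismatch over cycles bars and admits the same patient.* Not shown. Section 8.4.4 and the list in 7.3.2.11 do differ, but footnote l names no cycle. No patient is affected unless c exceeds about 0.607. Section 8.4.4 also requires imaging in anyone with symptomatic heart failure.
- *The 10% wording differs between sections.* It does not. All of them, and section 2.2, leave it undefined in the same way. It is a shared ambiguity.
- *Inclusion criterion 7 conflicts with the continuation rule.* An entry criterion need not share a threshold with a continuation rule. It matters here only because it lets a patient in at 50%.
- *The imaging methods conflict.* Section 7.3.2.14 names only echocardiography, but the schedule row that carries footnote l is labelled for echocardiography or MUGA. That largely answers the point.

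**Conclusion.** The point holds as a narrow contradiction in a safety rule. The continuation rule in 7.3.2.14 and footnote l and the stop in 8.4.4 disagree at an EF of exactly 50%, for baselines of 50% to 60% (points) or about 50% to 55.6% (relative), in patients above 550 mg/m² who are due consolidation. The documents do not allow an estimate of how many patients that is. Whether anyone passes 550 mg/m² by cycle 2 or 3 rests on the undocumented mg per unit, with limits of 0.423 and 0.325 at the entry cap.

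There are two lesser points. The undefined 10% touches more EF values than the boundary does, but it is an ambiguity, not a contradiction. The absent cardiac step in 7.3.2.11 is a real difference in the text with no demonstrated effect.

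A reader might infer damage to the main result. There is none: the primary endpoint is CR/CRi at day 28 of induction, before any consolidation rule applies, and the sample size does not depend on it. This is a minor but worthwhile correction.

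**What to change.** Reconcile section 7.3.2.14, footnote l and section 8.4.4 so that they carry one EF expression, with the permitting and stopping rules as exact complements. State once whether the 10% fall is in percentage points or relative to baseline, and use that meaning throughout. Make sections 7.3.2.11 and 8.4.4 agree on which consolidation cycles are checked. Stating the daunorubicin content per unit would let staff see when 550 mg/m² is reached.

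The threshold, the meaning of the fall and the cycles are clinical choices for the sponsor, and this review proposes none. Inclusion criterion 7 needs no change on this account. The cost is wording in a protocol amendment, with the IRB review that section 13.2 requires. The sample size and the primary analysis do not change.
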